6.2. WITHDRAWAL OF SUBJECTS

Subjects should be withdrawn from the study treatment for the any of the following reasons;

- At their own or legally acceptable representative request.
- At any time of subject's decision not to participate further.
- In case of investigator's decision that the continuation of study treatment would be harmful to the subject.
- Use of other substances or herbal medicines that may affect the treatment and the results of this study.
- Development of more beneficial treatment, by investigator's judgment, for the subject in the treatment continuum.
- Disease progression or unacceptable adverse events.
- Development of a secondary malignancy.
- Lost to follow-up.
- Interruption of study drug due to drug related adverse events is longer than 4 consecutive weeks.

6.3. REPLACEMENT

A subject withdrawn from the study treatment will not be replaced.

7. STUDY TREATMENT

7.1. DURVALUMAB

Durvalumab will be supplied by AstraZeneca as a 500-mg vial solution for infusion after dilution. The solution contains 50 mg/mL of durvalumab, 26 mM histidine/histidine-hydrochloride, 275 mM trehalose dihydrate, and 0.02% weight/volume (w/v) polysorbate 80; it has a pH of 6.0. The nominal fill volume is 10.0 mL. Investigational product vials are stored at 2°C to 8°C (36°F to 46 °F) and must not be frozen.

The dose of durvalumab for administration must be prepared by aseptic technique. Total in-use storage time from needle puncture of durvalumab vial to the start of administration should not exceed:

- 4 hours at room temperature
- 24 hours at 2°C to 8°C (36°F to 46°F).

Infusion solution must be allowed to equilibrate to room temperature prior to commencement of administration.

Preparation of durvalumab doses for administration with an IV bag

A dose of 1500 mg (for patients > 30 kg in weight) will be administered using an IV bag containing 0.9% (w/v) saline or 5% (w/v) dextrose, with a final durvalumab concentration ranging from 1 to 20 mg/mL, and delivered through an IV administration set with a 0.2- or 0.22µm in-line filter. Add 30.0 mL (1500 mg) of durvalumab to the IV bag. The IV bag size should be selected such that the final concentration is between 1 and 20 mg/ml. Mix the bag by gentle inversion to ensure homogeneity of the dose in the bag.

Weight-based dosing (for patients ≤ 30 kg) will be administered using an IV bag containing 0.9% (w/v) saline or 5% (w/v) dextrose, with a final durvalumab concentration ranging from 1 to 20 mg/mL, and delivered through an IV administration set with a 0.2- or 0.22-µm in-line filter. Appendix B includes an example of a weight-based dose calculation.

Standard infusion time is 60 minutes (± 5 minutes). Less than 55 minutes is considered a deviation. In the event that there are interruptions during infusion, the total allowed time should not exceed 8 hours at room temperature.

The IV line will be flushed with a volume of IV diluent equal to the priming volume of the infusion set used after the contents of the IV bag are fully administered, or complete the infusion according to institutional policy to ensure the full dose is administered and

document if the line was not flushed.

In the event that either preparation time or infusion time exceeds the time limits a new dose must be prepared from new vials. Durvalumab does not contain preservatives, and any unused portion must be discarded.

No incompatibilities between durvalumab and polyvinylchloride or polyolefin IV bags have been observed.

Monitoring of dose administration

Patients will be monitored during and after the infusion with assessment of vital signs at the times specified in the Study Protocol.

In the event of a \leq Grade 2 infusion-related reaction, the infusion rate of study drug may be decreased by 50% or interrupted until resolution of the event and re-initiated at 50% of the initial rate until completion of the infusion. For patients with a \leq Grade 2 infusion-related reaction, subsequent infusions may be administered at 50% of the initial rate. Acetaminophen and/or an antihistamine (eg, diphenhydramine) or equivalent medications per institutional standard may be administered at the discretion of the investigator. If the infusion-related reaction is \geq Grade 3 or higher in severity, study drug will be discontinued. For management of patients who experience an infusion reaction, please refer to the toxicity and management guidelines in [Appendix A](#).

As with any antibody, allergic reactions to dose administration are possible. Appropriate drugs and medical equipment to treat acute anaphylactic reactions must be immediately available, and study personnel must be trained to recognize and treat anaphylaxis. The study site must have immediate access to emergency resuscitation teams and equipment in addition to the ability to admit patients to an intensive care unit if necessary.

7.2. DOSE AND TREATMENT REGIMEN

Patients (> 30 kg in weight) will receive 1500 mg of durvalumab via intravenous infusion every 4 weeks. Patients (≤ 30 kg in weight) will receive weight based dosing of 20 mg/kg durvalumab via intravenous infusion every 4 weeks.

Durvalumab treatment can be continued up to the 36-cycle dosing. After 36 cycles of treatment, durvalumab should be discontinued.

7.3. DOSE MODIFICATION AND DELAYS

7.3.1. GENERAL RULES FOR DOSE MODIFICATION AND DELAYS

- Dose modification (reduction or escalation) is not allowed.
- Dose delays in case of clinically meaningful events are permitted; however, study treatment should be discontinued in case of 4 weeks delays.
- All the response evaluation procedures including CT scans should be performed as planned in patients with treatment delay without regard to the cycles of study treatment. Dose delays, reasons for treatment delay, actions to be taken and outcome will be recorded in patient chart and CRF.
- Regarding the adverse events, dose delays could be made under investigators' discretion.
- When the study treatment is restarted, the investigator should ensure that AE is recovered \leq grade 1 or there is no safety risk for the patients.
- Prophylactic use of G-CSF (or GM-CSF) or erythropoietin is not allowed.

7.4. LABELING

Labels will be prepared in accordance with Good Manufacturing Practice (GMP) and local regulatory guidelines. The labels will fulfil GMP Annex 13 requirements for labeling. Label text will be translated into local language.

Labels will be provided as either a single panel label or as multi-language booklet labels.

7.5. STORAGE

The Investigator, or an approved representative (eg, pharmacist), will ensure that all IP is stored in a secured area, in refrigerated temperatures (2°C to 8°C) and in accordance with applicable regulatory requirements. A temperature log will be used to record the temperature of the storage area. Temperature excursions outside the permissible range listed in the clinical supply packaging are to be reported to the monitor upon detection. A calibrated temperature monitoring device will be used to record the temperature conditions in the drug storage facility. Storage conditions stated in the IB may be superseded by the label storage.

7.6. COMPLIANCE

The administration of all study drugs (including IP) should be recorded in the appropriate sections of the eCRF. Treatment compliance will be assured by site reconciliation of medication dispensed and returned.

7.7. CONCOMITANT THERAPY

7.7.1. PROHIBITED CONCOMITANT MEDICATIONS

- Any investigational anticancer therapy other than those under investigation in this study.
- Any concurrent chemotherapy, immunotherapy or biologic or hormonal therapy for cancer treatment.
- Any concurrent radiotherapy is not permitted; however, if the local investigator decides that radiation therapy should be given during study treatments, he should be convinced that there is no evidence of disease progression and there is no target lesion(s) included in the field of radiotherapy with agreement of the chief principal investigator.
- Immunosuppressive medications including, but not limited to, systemic corticosteroids at doses exceeding 10 mg/day of prednisone or equivalent, methotrexate, azathioprine, and tumor necrosis factor- α blockers.
- Live attenuated vaccines are not permitted; inactivated vaccines (i.e. influenza vaccines) are permitted.
- Drugs with laxative properties and herbal or natural remedies for constipation.
- Prophylactic administration of G-CSF (or GM-CSF) or erythropoietin.
- All traditional medicines with an intention to control the tumor without regard to their truth

7.7.2. PERMITTED CONCOMITANT MEDICATIONS

- Standard therapies for treatment of concurrent medical conditions and complications or symptomatic therapy of adverse events are permitted.
- Blood transfusion.
- G-CSF (or GM-CSF) for febrile neutropenia or infection with neutropenia; however, the prophylactic use of these agents are not permitted even for 2nd occurrence without evidence of fever or infection.
- Antiemetics: as for acute nausea/vomiting, intravenous administration of 5-HT₃ antagonist can be considered, but not recommended routinely. Metoclopramide, lorazepam or corticosteroid might be used.
- Antidiarrheals: in general, loperamide is recommended as the standard treatment. Because any agents having purgative activity might aggravate diarrhea, its use should be avoided. Make patients contact with investigators about the use of a purgative.
- Antibiotics, analgesics, analgesic antipyretics, steroidal agents, opioids including morphine, fentanyl patches, etc.

7.8. RESTRICTIONS

The following restrictions apply while the patient is receiving study treatment and for the specified times before and after:

7.8.1. FEMALE PATIENT OF CHILD-BEARING POTENTIAL

- Females of childbearing potential who are sexually active with a non-sterilized male partner must use at least 1 **highly** effective method of contraception (Table 1) from the time of screening and must agree to continue using such precautions for 90 days after the last dose of durvalumab monotherapy. Non-sterilized male partners of a female patient must use male condom plus spermicide throughout this period. Cessation of birth control after this point should be discussed with a responsible physician. Not engaging in sexual activity for the total duration of the drug treatment and the drug washout period is an acceptable practice; however, periodic abstinence, the rhythm method, and the withdrawal method are not acceptable methods of birth control. Female patients should also refrain from breastfeeding throughout this period.

7.8.2. MALE PATIENT WITH A FEMALE PARTNER OF CHILDBEARING POTENTIAL

- Non-sterilized males who are sexually active with a female partner of childbearing potential must use a male condom plus spermicide from screening through 90 days after receipt of the final dose of durvalumab monotherapy. Not engaging in sexual activity is an acceptable practice; however, occasional abstinence, the rhythm method, and the withdrawal method are not acceptable methods of contraception. Male patients should refrain from sperm donation throughout this period.
Female partners (of childbearing potential) of male patients must also use a highly effective method of contraception throughout this period (Table 1). N.B Females of childbearing potential are defined as those who are not surgically sterile (ie, bilateral tubal ligation, bilateral oophorectomy, or complete hysterectomy) or post-menopausal. Women will be considered post-menopausal if they have been amenorrheic for 12 months without an alternative medical cause. The following age-specific requirements apply:
 - Women <50 years of age would be considered post-menopausal if they have been amenorrheic for 12 months or more following cessation of exogenous hormonal treatments and if they have luteinizing hormone and follicle-stimulating hormone levels in the post-menopausal range for the institution or underwent surgical sterilization (bilateral oophorectomy or hysterectomy).
 - Women ≥50 years of age would be considered post-menopausal if they have been amenorrheic for 12 months or more following cessation of all exogenous hormonal treatments, had radiation-induced menopause with last menses >1 year ago, had chemotherapy-induced menopause with last menses >1 year ago, or underwent surgical sterilization (bilateral oophorectomy, bilateral salpingectomy or hysterectomy).

Highly effective methods of contraception, defined as one that results in a low failure rate (ie, less than 1% per year) when used consistently and correctly are described in Table 1. Note that some contraception methods are not considered highly effective (eg. male or female condom with or without spermicide; female cap, diaphragm, or sponge with or without spermicide; non-copper containing intrauterine device; progestogen-only oral hormonal contraceptive pills where inhibition of ovulation is not the primary mode of action [excluding Cerazette/desogestrel which is considered highly effective]; and triphasic combined oral contraceptive pills).

Table 1. Highly effective methods of contraception (<1% failure rate)

Nonhormonal methods	Hormonal Methods

 • Total sexual abstinence (evaluate in relation to the duration of the clinical study and the preferred^{and} usual lifestyle choice of participant) • Vasectomised sexual partner (with participant assurance that partner received post-vasectomy confirmation of azoospermia) • Tubal occlusion: Intrauterine device (provided coils are copper-banded) 	
 • Implants: Etonogestrel-releasing implants (e.g. Implanon[®] or Norplant[®]) • Intravaginal device: Ethinylestradiol/etonogestrel-releasing intravaginal devices (e.g. NuvaRing[®]) • Injection: Medroxyprogesterone injection (e.g. Depo-Provera[®]) • Combined Pill: Normal and low dose combined oral contraceptive pill • Patch: Norelgestromin/ethinylestradiol-releasing transdermal system (e.g. OrthoEvra[®]) • Mini pill: Progestrone based oral contraceptive pill using desogestrel: Cerazette[®] is currently the only highly effective progesterone- based based • Levonorgestrel-releasing intrauterine system (e.g. Mirena[®])

7.8.3. BLOOD DONATION

Subjects should not donate blood while participating in this study, or for at least 90 days following the last infusion of durvalumab

7.9. POST-STUDY TREATMENT

All subjects will enter the follow-up period upon discontinuation of either randomized

study treatment. Regardless of the reason for discontinuation, all subjects will be followed for survival until death is documented, except for those who specifically withdraw consent to follow-up. Subjects who withdraw consent from study drug treatment may enter the Follow-up Period. Assessment of survival status will be performed approximately every 3 months. In addition, for subjects who discontinue study treatment and have not experienced PD, available tumor assessments will be recorded in the CRF until PD is documented. Additionally, the administration of any anti-cancer drugs must be recorded in the CRF.

8. STUDY PROCEDURE AND SCHEDULE

8.1. TABULATED OVERVIEW

Study Period	Screening	Study Treatment (-/+ 1 week)			Post Treatment (-/+ 2 weeks)
		Every cycle	Every 8 weeks	End of Treatment	Every 3 months
Study Procedures: Study Day:	D-14 to -1				
Informed consent	○				
Inclusion/Exclusion criteria review	○				
Demographics; medical history	○				
Complete physical examination	○	○		○	
Vital Signs	○	○		○	
ECOG performance status	○	○		○	
Electrocardiography ¹⁾	○			○	
Concomitant medication	○	○		○	
Chest X-ray	○		○	○	
Tumor Assessment (CT or MRI)	○		○	○	
Other imaging procedure if needed	○		○	○	
Assessment of response			○	○	
Toxicity assessment (CTCAE version 4.0)		○		○	
Survival					○
Subsequent treatment					○
CBC	○	○		○	
Chemistry ²⁾ , Amylase/Lipase	○	○		○	
CEA	○		○	○	
Thyroid function test (TSH, T3, free	○		○		

T4)					
Routine urinalysis	O				
Urine β -hCG pregnancy test ³⁾	O				
Height (screening only)/Weight	O	O		O	
Biomarker assessment ⁴⁾	O				

1) In patients without prior history of cardiovascular disease and showed normal electrocardiography, further examinations such as MUGA scan and echocardiography are not mandatory; however, patients with prior history of cardiac disease or those showed abnormal electrocardiography results, they would be checked with further examinations either with MUGA scan or echocardiography by the investigator's decision.

2) Chemistry labs include calcium, phosphorus, glucose, BUN, creatinine, total protein, albumin, AST/ALT, alkaline phosphatase, total bilirubin, uric acid and electrolytes(Na, K, Cl, Mg).

3) Urine β -hCG should be performed in women with child-bearing potential.

4) Perform tests for pertinent tumor markers if informative in the investigator's opinion and document at screening or as clinically indicated.

8.2. EVALUATION BEFORE STUDY TREATMENT (WITHIN 2 WEEKS)

- Complete medical history.
- Physical examination including ECOG performance status.
- Radiologic assessments using RECIST 1.1. (permitted to be assessed within 28 days from the study treatment)
- CBC with differentials.
- Serum chemistry: calcium, phosphorus, glucose, BUN, creatinine, total protein, albumin, AST/ALT, alkaline phosphatase, total bilirubin, uric acid and electrolytes.
- Routine urinalysis
- Serum CEA
- Serum TSH, T3 and free T4
- Serum amylase/lipase
- EKG (3 consecutive EKG for eligibility check)
- Chest X-rays
- Urine β -hCG will be performed in women with child-bearing potential.
- Other tests (i.e. bone scans) if clinically indicated
- Exploratory biomarker assessments:
 - Opal Multiplex Tissue Staining with Opal™ including PD-1 and PD-L1
- Biological samples will be obtained for biomarker evaluation from all eligible patients at the screening visit.

8.3. EVALUATION DURING STUDY TREATMENT (EVERY CYCLES OF STUDY TREATMENT)

- Physical examination including ECOG performance status and drug-related side effects.
- CBC with differentials.
- Serum chemistry: calcium, phosphorus, glucose, BUN, creatinine, total protein, albumin, AST/ALT, alkaline phosphatase, total bilirubin, uric acid and electrolytes.
- Serum amylase/lipase
- Toxicity assessments (NCI-CTCAE version 4.0)

8.4. RESPONSE EVALUATION (EVERY 8 WEEKS ± 1 WEEK WINDOW PERIOD)

- Serum CEA, TSH, T3 and free T4
- CT (or MRI) scans of evaluable/measurable lesions by RECIST 1.1.
- Other test (i.e. bone scans) if clinically indicated
- Response evaluation will be performed every 8 weeks without regard to the schedules of study treatment.

8.5. POST-TREATMENT FOLLOW-UP (EVERY 3 MONTHS)

- Subsequent treatments (chemotherapy, immunotherapy or radiotherapy) and their responses
- Survival information on subject
- Status of disease and date of progression (in patients who stopped study treatment without documentation of disease progression)
- Date and cause of death

Telephone follow-up is acceptable. Site staff must use caution when contacting the subject's family for this information, especially if they are no longer under the care of the investigator, so as to not inadvertently cause any distress to the family of a subject who is no longer alive. Additional phone contacts will be required for formal survival sweeps at the time of primary analysis.

9. ADVERSE EVENTS

9.1. DEFINITIONS

9.1.1. ADVERSE EVENT

The term **adverse event** covers any unfavorable and unintended sign, symptom, syndrome,

or illness that develops or worsens during the period of observation in the clinical study. Clinically relevant abnormal results of diagnostic procedures including abnormal laboratory findings (e.g., requiring unscheduled diagnostic procedures or treatment measures, or resulting in withdrawal from the study) are considered to be adverse events.

Worsening of a sign or symptom of the condition under treatment will normally be measured by safety parameters. However, if the outcome fulfills the definition of «serious adverse event», it must be recorded as such.

The adverse event may be:

- A new illness
- Worsening of a concomitant illness
- An effect of the study medication, including comparator
- A combination of two or more of these factors
- No causal relationship with the study medication or with the clinical study itself is implied by the use of the term «adverse event».
- Adverse events fall into the categories «non serious» and «serious».

Surgical procedures themselves are not adverse events; they are therapeutic measures for conditions that require surgery. The condition for which the surgery is required is an adverse event, if it occurs or is detected during the study period. Planned surgical measures permitted by the clinical study protocol and the condition(s) leading to these measures are not adverse events, if the condition(s) was (were) known before the start of study treatment. In the latter case the condition should be reported as medical history.

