9.1.2. SERIOUS ADVERSE EVENTS

A serious adverse event is one that at any dose (including overdose):

- Results in death
- Is life-threatening ¹
- Requires in-patient hospitalization or prolongation of existing hospitalization
- Results in persistent or significant disability or incapacity ²
- Is a congenital anomaly or birth defect
- Is an important medical event ³

¹ «Life-threatening» means that the subject was at immediate risk of death at the time of the serious adverse event; it does not refer to a serious adverse event that hypothetically might have caused death if it were more severe.

² «Persistent or significant disability or incapacity» means that there is a substantial

disruption of a person's ability to carry out normal life functions.

³ Medical and scientific judgment should be exercised in deciding whether expedited reporting is appropriate in situations where none of the outcomes listed above occurred. Important medical events that may not be immediately life-threatening or result in death or hospitalization but may jeopardize the subject or may require intervention to prevent one of the other outcomes listed in the definition above should also usually be considered serious. Examples of such events include allergic bronchospasm requiring intensive treatment in an emergency room or at home, blood dyscrasias or convulsions that do not result in in-patient hospitalization, or the development of drug dependency or drug abuse. A diagnosis of cancer during the course of a treatment should be considered as medically important. The List of Critical Terms (1998 adaptation of WHO Adverse Reaction Terminology Critical Terms List, provided in the «Instructions for completing the 'Serious Adverse Event/Expedited Report from a Clinical Trial' form») should be used as guidance for adverse events that may be considered serious because they are medically important.

Clarification of the difference in meaning between «severe» and «serious»:

The term «severe» is often used to describe the intensity (severity) of a specific event (as in mild, moderate, or severe myocardial infarction); the event itself, however, may be of relatively minor medical significance (such as severe headache). This is not the same as «serious», which is based on the outcome or action criteria usually associated with events that pose a threat to life or functioning. Seriousness (not severity) serves as a guide for defining regulatory reporting obligations.

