9.1.4. RECORDING OF ADVERSE EVENTS AND SERIOUS ADVERSE EVENTS

Adverse events will be recorded CRF using a recognized medical term or diagnosis that accurately reflects the event. Adverse events will be assessed by the investigator for severity, relationship to the investigational product, possible etiologies, and whether the event meets criteria of an SAE and therefore requires immediate notification to AstraZeneca/MedImmune Patient Safety.

The following variables will be collected for each AE:

- AE (verbatim)

- The date <<and time>> when the AE started and stopped
- Changes in NCI CTCAE grade and the maximum CTC grade attained
- Whether the AE is serious or not
- Investigator causality rating against durvalumab (yes or no)
- Action taken with regard to durvalumab /comparator/combination agent
- Outcome

In addition, the following variables will be collected for SAEs as applicable:

- Date AE met criteria for serious AE
- Date Investigator became aware of serious AE
- AE is serious due to <<criteria>>
- Date of hospitalization
- Date of discharge
- Probable cause of death
- Date of death
- Autopsy performed
- Description of AE
- Causality assessment in relation to Study procedure(s)

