10.3. STATISTICAL PARAMETERS AND STATISTICAL ANALYSIS PLAN

Safety analysis will be conducted in the safety analysis set. Safety evaluation will include all patients who receive at least one dose of study drug. The safety analysis is based on the abnormality of laboratory test and clinical adverse events. Considering the percentage of laboratory abnormalities or clinical adverse events, descriptive statistics (or Fisher's exact test, Chi-square test for comparison between parameters) will be used. The primary endpoint, the objective response rates, will be described with percentage (%) and 95% confidence intervals. The survival outcomes, secondary endpoints, will be calculated using Kaplan-Meier method, compared using long-rank test and described with 95% confidence intervals. The disease-control rates will be described with percentage (%) and 95% confidence intervals, and compared using odds ratio and Chi-square tests. The Kaplan-Meier method will be used to estimate progression-free and overall survival curves, and the Cox proportional hazards regression model will be used for multivariate analysis of prognostic factors for survival outcomes.

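### Section 9.1.1 places worsening signs and symptoms of the treated cancer under safety, against its own context, and section 10.3 plans no treatment-related summary that would show the effect

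*Combined protocol and SAP*

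**What the plan says.** Section 9.1.1 defines an AE broadly. It covers any unfavourable sign, symptom, syndrome "or illness that develops or worsens during the period of observation in the clinical study", with no carve-out for the cancer under study. It then turns to the treated disease: "Worsening of a sign or symptom of the condition under treatment will normally be measured by safety parameters". The next sentence reads: "However, if the outcome fulfills the definition of «serious adverse event», it must be recorded as such". The list of what an AE may be includes "Worsening of a concomitant illness" but does not mention the condition under treatment.

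Sections 4.1 and 4.2 measure the course of the cancer through RECIST 1.1 response, irRECIST response, disease control, PFS and OS. Section 8.4 schedules scans every 8 weeks. Safety and toxicity is a secondary objective.

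On analysis, section 10.3 says: "The safety analysis is based on the abnormality of laboratory test and clinical adverse events". It plans percentages with descriptive statistics. It does not mention the yes/no causality rating against durvalumab that section 9.1.4 collects for each AE, or the cause of death collected under sections 9.1.4 and 8.5.

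**The concern.** The sentence about the treated disease appears to carry the wrong word. If worsening of the cancer were already a safety matter, there would be no reason to follow it with a contrasting sentence that brings serious outcomes into safety recording.

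A site that takes the text as it stands can enter tumour pain or another symptom of progression as an AE. A site that reads it in context may not. The AE percentages of a multicentre, single-arm trial would then depend partly on how each site read one sentence and partly on how well the tumour was controlled. There is no control arm to show the disease background, and the planned summary has no treatment-related row to set beside the total.

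**Working it through.** **The texts side by side**

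1. Section 9.1.1, sentence on the treated condition: worsening signs and symptoms normally go to safety parameters.
2. Section 9.1.1, next sentence: it opens with a contrast and requires a serious-AE record when the outcome is serious. The contrast works only if non-serious worsening is normally measured elsewhere, that is, as efficacy.
3. Section 9.1.1, AE list: it names a concomitant illness only. This also points to efficacy for the treated disease.
4. Sections 4.1, 4.2, 8.4 and 10.3: worsening of the cancer is already measured by scans, response, disease control, PFS and OS.
5. Appendix A, table of non-immune-mediated reactions: events due to underlying disease are treated as a kind of unrelated AE. No section takes progression out of the AE count.

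Item 1 therefore conflicts with items 2 to 4, and nothing elsewhere settles the matter for non-serious events.

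**What does not depend on the sentence**

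Serious outcomes enter separately. Section 9.1.2 lists "Results in death" and hospitalisation as criteria. Section 9.2 requires all serious AEs to be reported whatever their cause, from consent to 90 days after the last dose or until other anticancer therapy starts. Changing the word would leave these events where they are.

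**How many patients could be affected**

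The plan states no figure for this. The inputs are:

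- Planned accrual (section 5.1): 17 MMR deficient or microsatellite instable, 16 *POLE* mutated, 33 in total.
- Share free of progression at 20 weeks in the cited pembrolizumab trial (section 3.1): 78% MMR deficient, 11% MMR proficient. The shares progressing are 1 − 0.78 = 0.22 and 1 − 0.11 = 0.89.
- Assumptions: these rates carry over to durvalumab; *POLE* mutated tumours behave somewhere between the two groups; only patients who progress have worsening signs or symptoms of the cancer; all 33 are treated.

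Expected number progressing by week 20 = 17 × 0.22 + 16 × q, where q is the *POLE* progression share:

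| *POLE* behaves like | q | Calculation | Of 33 |
|---|---|---|---|
| MMR deficient | 0.22 | 3.74 + 3.52 = 7.26 | 22% |
| MMR proficient | 0.89 | 3.74 + 14.24 = 17.98 | 54% |

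Under these assumptions the range is an upper bound on patients affected by week 20. A progression on a scan need not bring a worsening sign or symptom, and not every site would record one as an AE.

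**Primary design**

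Exact binomial calculation for the design in section 10.2 (continue with at least 2 responses in 10, succeed with at least 6 in 29) gives a type I error of 0.0471 at a 10% response rate and power of 0.8051 at 30%. With 10% dropout, 29 / 0.9 = 32.2, rounded up to 33. The plan's figures reproduce, and AE wording enters none of them.

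**The case against.** The strongest reply is that context already settles the meaning. The sentence speaks of a sign or symptom, says normally, and says measured; it does not say that progression is recorded as an AE. Sites also follow CRF instructions that are not part of these documents. The data can separate disease from toxicity: causality is rated for each AE, cause of death is collected, section 8.3 checks drug-related side effects each cycle, and section 9.1.3 asks that neoplastic causes be ruled out before an immune-related event is diagnosed. Section 10.3 does not forbid a treatment-related table.

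Most of this stands, and it limits the point. Four stronger conclusions that a reader might draw are not supported:

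- *Progression is counted as an AE.* The text allows that reading but does not state it.
- *Cancer deaths enter the AE percentages because of this sentence.* They become serious AEs through the next sentence and sections 9.1.2 and 9.2, and only inside the reporting window. Subtracting median PFS from median OS in Figure 2 (3.3 to 5.6 months) and applying 1 − 2^(−(90/30.44)/m) would suggest that 46% to 31% die within 90 days of progression. That treats a difference of medians as a median, assumes exponential survival, borrows other drugs' and placebo arms, and starts the clock at progression instead of the last dose.
- *Reported grade 3 or higher toxicity would rise from an assumed 10% to between 1 − 0.90 × 0.78 = 30% and 1 − 0.90 × 0.455 = 59%.* This needs every progression to be recorded as an AE at grade 3 or higher and to be independent of toxicity. Nothing in the documents supports that.
- *The trial cannot say how toxic durvalumab is.* The causality rating lets it do so; section 10.3 merely does not plan the table.

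The reply does not remove the contradiction in the operative text, the room for sites to differ, or the missing summary.

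**Conclusion.** The point holds as a contradiction in wording joined to a thin safety analysis plan. Read literally, section 9.1.1 lets non-serious signs and symptoms of progressing colorectal cancer be recorded as AEs, and section 10.3 would report them in the same percentages as drug toxicity without a treatment-related figure beside them.

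The size of the distortion cannot be fixed from the documents. The bound of 22% to 54% of patients by week 20 rests on another drug's rates, an assumed range for *POLE* mutated tumours, and worsening confined to patients who progress; it is not an estimate of inflated toxicity. The effect is confined to a secondary, descriptive objective. The response test, type I error, power and sample size do not change. It should be corrected because it affects what sites record and how a single-arm safety summary is read.

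**What to change.** In section 9.1.1, change *safety parameters* to *efficacy parameters* in the sentence on the treated condition. Leave the following sentence and all serious-AE reporting unchanged.

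In section 10.3, add that AE percentages will be shown for all causes and, beside them, for events rated as related to durvalumab under section 9.1.4. List serious AEs and deaths due to disease progression on a separate line, using the cause-of-death fields and the serious-AE descriptions already collected. Remove no event from the all-cause total: excluding events judged to be due solely to progression would put an open-label investigator judgement inside the main safety figure, and the side-by-side tables make that unnecessary.

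The cost is one word, one or two sentences and one or two table rows from existing data. Two limits remain. The causality rating is itself an open-label investigator judgement, which is why the all-cause total stays beside it. The wording change also reaches only records made after it; the tables cover events already recorded.
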